The main goal of this project is to measure kidney filtration function at day 14 of the ICU stay or the day of discharge from the ICU (whichever occurs first), in order to determine the presence and *magnitude of persistent kidney dysfunction after sepsis episode and to longitudinally assess* further decline of kidney function at one year follow-up. In our initial IRB protocol we have proposed to use iohexol clearance as a gold standard that provides most accurate determination of glomerular filtration rate (GFR). Unfortunately we have not been able to recruit patients into the study as designed due to the complexity of this procedure and need for a dedicated IV line. Since one of the main goals of the overall project is to determine the decline in glomerular filtration rate from the sepsis episode to the one year follow up, we have considered different approaches, in order to be able to obtain this valuable data.

We propose to offer patients four complementary ways for GFR assessment, both at approximately day 14 or approximately at the day of discharge from the ICU and at the one year follow up :

1. Determine clearance of iohexol from blood after iohexol injection and/or
2. Determine appearance of iohexol in urine after iohexol injection (this would be the same injection as in one, and would not require two injections) and/or
3. A timed urine collection to determine clearance of urea and creatinine and/or
4. Estimated GFR using calculations with serum creatinine, if performed clinically if not we will draw it specifically for the study, and cystatin C, performed specifically for the study. Currently any patient that is enrolled in this protocol will already be a part of IRB201400611 and will already be getting serum creatinine, cystatin C and a urine microalbumin/creatinine ratio drawn at the one year appointment.

This approach will allow us to maximize recruitment of patients into the study by providing flexibility, but it also provides an important opportunity to validate the different measurements against the gold standard, iohexol clearance. For all patients we will also obtain a urine microalbumin/creatinine ratio as another important determinant of structural kidney damage.

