We also propose to include stage 3 AKI patients on renal replacement therapy, who were previously excluded. Some of these patients do recover after initial episode and will present at one year follow up. It will be very valuable for us to understand factors leading to recovery. For these patients we will use only methods 2 and/or 3 for estimation of GFR, both of which are safe. Even patients who are dialysis dependent have some level of residual renal function and even if they make even a minimal amount of urine this may be an important determinant of renal recovery.

The assessments will be performed approximately 72 hours within day 14 or the anticipated discharge from the ICU and at 1 year follow-up.

Given the loss of muscle mass in chronic critical illness, we will measure, rather than estimate glomerular filtration rate, to determine whether unrecognized kidney dysfunction in late sepsis drives inflammation and catabolism, contributing to poor long term survival and development of chronic kidney disease. For the assessment of glomerular filtration rate, the most frequently used clinical test is serum creatinine, despite the fact that its accuracy depends on a constant muscle mass, which is almost never the case with patients with chronic critical illness. We have previously demonstrated that sepsis and chronic critical illness are associated with a rapid and significant loss of lean muscle mass over time. Even a small fall of 25% in muscle mass should lead to a fall in serum creatinine of 25%. Thus in a chronic critical illness patient hospitalized for 4 weeks, the persistent increase in serum creatinine from a baseline of 1.0 mg/dl to 1.5 mg/dl implicates a significant drop in glomerular filtration rate; assuming a 50% reduction in muscle mass, in this individual a serum creatinine of 1.5 would reflect glomerular filtration rate of ~ 37 mL/min/1.73 m², consistent with stage 3 chronic kidney disease. To determine whether unrecognized decline in kidney function contributes to persistent inflammation, decreased protein intake, and muscle wasting in chronic critical illness it is necessary to measure glomerular filtration rate rather than estimate it.

5. Specific Aims:

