Iohexol clearance will not be performed in patients with a known allergy to contrast. All patients will need two IVs for this procedure. If the subject does not have 2 intravenous catheters (IVs) as a part of their routine clinical care during sepsis episode they will be placed by someone from the research team. We will attempt to place a 22 gauge or larger IV as indicated by the patients veins. We will inject iohexol 0.5-1 ml of iohexol diluted in normal saline through an existing IV catheter, and we will collect no more than 3 ml of blood prior to the injection and at approximately 1, 2, 3 and 4 hours after injection. The concentration of iohexol in the blood will be measured by ELISA (Biopal Inc). The GFR will be calculated by the blood clearance method:

The concentration of iohexol ($\mu\text{g}/\text{ml}$) in each blood sample will be plotted as a function of time. The data will be fit to a one exponential decay function, i.e., $Y = B e^{-bX}$. The function will be integrated over the limits zero to infinity to obtain the area-under-the-curve (AUC), i.e., $AUC = B/b$ ($\text{mg}\cdot\text{min}/\text{ml}$). The GFR value (ml/min) is then obtained by dividing the administrated dose by the AUC (REF:

2. Timed urinary collection for combined urea and creatinine clearance.

The urine will be collected for at least 4 hours to as long as 24 hours or more. The urine volume determined and a sample sent to the lab for determination of creatinine and urea concentration. We will not place a foley if there is not a foley and the person will only be asked to collect their urine for the indicated time.

3. Estimation of GFR using serum creatinine and cystatin C. We will estimate GFR using both serum creatinine and cystatin C and average the two values using CKD-EPI equation.

The glomerular filtration rate at 1 year will be compared to the measured glomerular filtration rate at discharge and the rate of change in glomerular filtration rate over time will be determined. The measured iohexol glomerular filtration rate will be compared to the estimated glomerular filtration rate, as determined by the in order to correlate the equation after adjusting for loss of muscle mass.

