The patients will be asked to return for a one year follow up appointment that will occur with the one year appointment from IRB protocol #2014-611 at the Institute on Aging. The patients will receive a \$25 compensation for the inpatient portion of the study and a \$75 compensation for their time when they return for the one year follow up visit. At one year follow-up all measurements for iohexol clearance, will be performed in CTSI. Timed urine collection at one year follow up will be performed at home and all necessary supplies will be mailed to patient. If the patient did not do a timed collection, but is still willing to perform timed urine at the time of the CTSI visit, we will time the urine collection during their CTSI visit. For patients who opt only for serum creatinine/cystatin C measurement and spot urine microalbumin/creatinine ratio, urine and blood will be collected in the CTSI as a part of the IRB protocol #2014-611.

Primary Outcomes

We will compare:

Protocol

IRB version 03.09.04

PI version 9/10/2015

- a) The decline in glomerular filtration rate at 1-year follow-up between chronic critical illness and control groups.
- b) Correlation between iohexol glomerular filtration rate and estimated glomerular filtration rate using previously validated equation applied to serum creatinine.
- c) Development of de novo albuminuria or progression of existing albuminuria.

Data Collection and Analyses

All relevant clinical and laboratory variables for this cohort will be uploaded directly into the REDCap case report form (CRF) from the EPIC EMR for the main STUDY IRB#2014-611.

Sample size and feasibility. Assuming that chronic critical illness patients have at least a two-fold decline in glomerular filtration rate as compared to the average glomerular filtration rate decline of 6 ± 16 ml/yr, the sample size of 150 chronic critical illness and 80 control subjects will offer 80% power at a two-sided significance of $P=0.05$.

Data analyses and interpretation. The parametric and non-parametric tests for difference between two independent samples will be used to compare decline in glomerular filtration rate between chronic critical illness. Using the Cox survival model we will test the multivariate relationship between glomerular filtration rate at day 14 and survival status at year 1.

Protection of Privacy and Confidentiality

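### The written blood-iohexol GFR rule carries one exponential from samples at about 1 to 4 hours back to time zero with no stated early-phase correction, so it reads high if iohexol has a distribution phase

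*Combined protocol and SAP*

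**What the plan says.** Section 6, under Iohexol clearance, specifies blood draws of "no more than 3 ml of blood prior to the injection and at approximately 1, 2, 3 and 4 hours after injection". The calculation follows: "The data will be fit to a one exponential decay function", written Y = B e^(-bX). Then "The function will be integrated over the limits zero to infinity to obtain the area-under-the-curve (AUC" = B/b), and GFR is the dose divided by that area. The reference for the method breaks off in the available text. No sample between injection and about 1 hour, no second exponential and no correction factor is written. All concentrations are to be plotted against time, and the pre-injection sample is given no stated role.

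The result is used in three places:

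- Section 4 says that offering several methods is an opportunity to "validate the different measurements against the gold standard, iohexol clearance".
- Section 6, under Estimation of GFR, says "The measured iohexol glomerular filtration rate will be compared to the estimated glomerular filtration rate". Primary outcome (b) makes that comparison a correlation.
- Primary outcome (a) is "The decline in glomerular filtration rate at 1-year follow-up between chronic critical illness and control groups".

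Iohexol is one of four methods that patients may combine or choose between. Section 4 limits patients on renal replacement therapy to methods 2 and/or 3, which leaves out blood clearance.

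**The concern.** A one-exponential fit gives the correct area only if the tracer mixes at once into a single volume. If it first distributes into a second volume, concentrations in the first hour lie above the line extrapolated back from later samples. The written area then omits that part, and dose divided by too small an area is too large a GFR. If distribution is still running at 1 hour, the fitted slope is also too steep.

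What is at stake is mainly the level of the reference standard. If iohexol reads high, an estimating equation that is correct on average would look as if it read low, and a correlation would not show it. The decline in outcome (a) could also be rescaled, because the error depends on the GFR level.

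**Working it through.** **Inputs from the protocol.** Post-injection times 60, 120, 180 and 240 min; one exponential; area B/b; GFR = dose × b/B. Sample size paragraph: average decline 6 ± 16 ml/yr and at least two-fold in chronic critical illness, so declines of 12 and 6 and a difference of 6.

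**Assumptions (not in the protocol).** Two compartments of 8 L each, exchange 100, 200, 300 or 400 ml/min, noise-free curves, log-linear fit.

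**1. Algebra.** The integral of B e^(-bX) from zero to infinity is B/b, so the formula is internally correct. With one-compartment data it returns the true GFR exactly (30, 60 and 100). Without a distribution phase there is no bias.

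**2. Lost area alone.** If the early phase is over by 1 hour and holds a share f of the true area, reading/true = 1/(1 − f). For f = 5%, 10% and 20% the reading is 5%, 11% and 25% high.

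**3. Full fit.** Example at true GFR 60 and exchange 200: fitted b = 0.003790 per min and B = 0.00005677 per ml per unit dose, so b/B = 66.8. The early phase holds 8.0% of the area, and 60/(1 − 0.080) = 65.2, so most of the excess here is lost area and the rest is slope.

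| True GFR | exch. 100 | 200 | 300 | 400 |
|---|---|---|---|---|
| 30 | 43.6 | 34.1 | 31.4 | 30.7 |
| 37 | 51.0 | 41.5 | 38.8 | 38.0 |
| 60 | 76.8 | 66.8 | 63.6 | 62.5 |
| 100 | 128.0 | 114.7 | 109.6 | 107.0 |

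Every reading is high. The size depends on the assumed volumes: with 8 L + 12 L and exchange 100, true 60 reads 90.2.

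**4. Outcome (b).** Simulation with 20,000 subjects, GFR mean 70, SD 25, estimate error SD 19 (all assumed). The correlation is 0.793 with true GFR and 0.791 to 0.793 with the written formula. Mean iohexol minus estimated GFR is 0.2 with true GFR, but 20.5, 9.4, 5.6 and 4.0 at exchange 100, 200, 300 and 400. The correlation misses the shift and the mean difference shows it.

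**5. Outcome (a), distribution unchanged, true difference 6.** At exchange 200:

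- Both groups start at 60 (60 to 48 against 60 to 54): (66.75 − 53.39) − (66.75 − 60.02) = 6.63. Over the four exchange rates: 6.78, 6.63, 6.51, 6.40.
- Different starts (50 to 38 against 90 to 84): (55.58 − 42.56) − (102.19 − 94.86) = 13.02 − 7.33, about 5.7. Over the four rates: 5.30, 5.68, 5.87, 5.94.

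**6. Outcome (a), volume change between visits.** Let g1 and g2 be the reading functions at the ICU visit and at one year. The group difference is [g1(start, cases) − g2(end, cases)] − [g1(start, controls) − g2(end, controls)]. If both groups share the same change and start at the same GFR, the g1 terms cancel and the difference stays at 6.4 to 6.8. They do not cancel if the change differs between groups or the starting GFRs differ.

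**7. Pre-injection sample.** If a residual concentration C0 decays at the fitted rate b, the area due to the study dose is (B − C0)/b, so GFR = dose × b/(B − C0). Left uncorrected, the reading is GFR/(1 + R) with R = m × exp(−GFR × t/15000), where 15 L is assumed and m = 10 to 100 is the inverse of the dose ratio in the safety monitoring plan. True 30 at 48 h (2,880 min): exp(−5.76) = 0.00315, so R = 0.0315 to 0.315 and the reading is 29.1 to 22.8. True 60 at 48 h and m = 100 reads 59.9.

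**8. Trial of a fixed correction.** Corrected = x − kx², with k = 0.00152 assumed so that true 60 at exchange 200 is exact. True 60 then reads 67.8, 60.0, 57.5 and 56.6. Over the 16 cells of the table the mean level error falls from about 14.5% to 8.3%, but at exchange 400 true 60 goes from 62.5 to 56.6. The difference of 6 becomes 5.4 to 5.5 (equal starts) or 5.6 to 6.1 (different starts). The mean differences in step 4 become 6.7, −1.4, −4.2 and −5.4.

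**The case against.** The strongest reply is that the defect may be only one of documentation. The formula sentence ends in a broken reference, and a correction could be in the cited method. The protocol says nothing of a distribution phase, so both premise and size come from outside it. This stands. The finding is that no correction is written and that the rule as written reads high if there is such a phase.

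The written outcomes also move little. The correlation is unchanged, and the decline difference moves from 6 to between 5.3 and 6.8 against a stated SD of 16, in a direction that depends on where the groups start. This stands too. Reach may be small: "Unfortunately we have not been able to recruit patients into the study as designed" is the protocol's account of the original iohexol design.

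Three stronger readings are tempting and are not supported:

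- A reader might infer that patients will be put in the wrong kidney-disease stage, because Section 4 calls a GFR of about 37 "consistent with stage 3 chronic kidney disease". That passage illustrates how serum creatinine misleads after muscle loss. It is not an iohexol reading, and the plan sets no iohexol cut-off.
- A reader might infer a large false decline in outcome (a) if excess fluid at the ICU visit resolves by one year. Outcome (a) is a between-group comparison, a shared change cancels at equal starting GFR, and the protocol gives no volumes.
- A reader might infer that earlier contrast studies pull first-visit readings down. The safety monitoring plan says most patients will have had one, but gives no agent or timing, and at true GFR 60 after 48 hours the modelled effect is negligible.

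Finally, the tested correction does not help everywhere. It is worse than none for true 60 at exchange 400 and does not make the decline exact. That limits the remedy to a prespecified correction reported beside the uncorrected value.

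**Conclusion.** The point holds in conditional form. The written rule omits any early-phase area, and if iohexol has a distribution phase it biases the reference standard upward: true 60 reads 62.5 to 76.8 under the assumed model. The direction was the same in every two-compartment run; the size cannot be fixed from the documents.

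It matters mainly for the validation aim, where a level shift of about 4 to 20 ml in the simulation leaves the correlation at 0.79. The effect on outcome (a) is modest when distribution is unchanged. A volume change between visits biases outcome (a) only if it differs between groups or the groups start at different GFRs, and a fixed correction cannot remove that bias. The unstated role of the pre-injection sample is a separate and smaller gap. None of this invalidates the study, and the number of patients affected is unknown. Confidence is medium because of the cut-off reference and the assumed kinetics.

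**What to change.** - State that only the post-injection samples enter the fit, and use the pre-injection sample as a blank: GFR = dose × b/(B − C0).
- Prespecify one published slope-intercept correction for the early phase (Brochner-Mortensen type), or write out the one in the cut-off reference. Apply it at both visits.
- Report GFR level and decline with and without the correction.
- Report the mean iohexol-minus-estimated difference beside the correlation in outcome (b).

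The cost is a few lines of calculation and no extra patients or samples, since the pre-injection sample is already drawn. There are two downsides. A fixed correction can over-correct when distribution is fast (56.6 instead of 62.5 for a true 60 at exchange 400). Baseline subtraction is imprecise when C0 is a large share of B: with an assumed 5% assay error, a true 30 has a 90% range of 18.5 to 84.8 at C0/B of 0.85, against 23.4 to 35.2 at 0.24 and 22.7 to 35.9 with no residual contrast. Reporting C0/B with each value would let readers see which results are affected.

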For the current study we have developed additional data and safety monitoring plan. The study involves more than minimal risk related to intervention for the routine standard measurement of glomerular filtration rate using iohexol. In addition, the study includes patients with a highly morbid pre-existing medical disease (sepsis), some of who are vulnerable subjects (chemically sedated in ICU due to primary disease sepsis). Thus physical, social, psychological, or financial events that are anticipated due to subjects' pre-existing disease including debilitated state, acute kidney injury, prolonged hospitalization, incapacity and death are possible and will be treated by the standard clinical care.

Safety and data integrity for this study will be assessed by PIs and the P50 investigator team led by program director [name] at weekly Adjudication meetings, IRB, GCRC Data Safety Monitoring Subcommittee and Internal Medical monitors for entire P50 program ([name], M.D., Professor of Surgery; [name], M.D., Professor of Anesthesiology, UF (Gainesville)). Accumulating study-wide data across all subjects will be monitored weekly and discussed at the weekly P50 meeting. Accumulated data will be discussed every three months at the P50 safety meeting. The following safety endpoints are in place: An MD is required to perform every injection and observe the patient for at least 15 minutes. If a side effect occurs as a result of the injection, we will formally present the case at the P50 weekly meeting. Importantly, the iohexol used for GFR measurement is routinely used clinically and we are using a 1/10 to 1/100 of the dose that is routinely used clinically, thus risks of side effects are greatly reduced. In addition the majority of these patients would have already received at least one contrast study during their hospitalization making it extremely unlikely to have undetected allergy to contrast. With any side effect suspected to occur as the result of the GFR determination, we will stop further GFR studies until the event can be presented and discussed at the weekly P50 meeting. Following adverse events will be observed: shortness of breath, itching, hives, vomiting, swelling, breathing difficulties, hypotension or any other noted problem related to the injection. They will be identified and monitored using advance monitoring system in ICU and GCRC as summarized in the table below

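### The plasma iohexol GFR formula has no term for contrast already in the blood, so a recent clinical iohexol scan would make the index GFR read low in patients with low GFR

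*Combined protocol and SAP*

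**What the plan says.** Protocol section 6, under Iohexol clearance, draws "no more than 3 ml of blood prior to the injection and at approximately 1, 2, 3 and 4 hours after injection". The concentration "in each blood sample will be plotted as a function of time". Then "The data will be fit to a one exponential decay function", Y = B·e^(-bX). Its integral from zero to infinity is AUC = B/b, and "The GFR value (ml/min) is then obtained by dividing the administrated dose by the AUC". The dose here is the study injection. The text does not say what the pre-injection value is for.

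The data and safety monitoring plan in section 7 says that "the majority of these patients would have already received at least one contrast study during their hospitalization", that iohexol is in routine clinical use, and that "we are using a 1/10 to 1/100 of the dose that is routinely used clinically". It raises prior contrast only as reassurance about undetected allergy.

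The restrictions on the iohexol test are contrast allergy, pregnancy and breastfeeding. In addition, section 4 (Background) keeps patients on renal replacement therapy off the plasma method. No section mentions the time since clinical contrast or asks for it to be recorded.

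**The concern.** If clinical iohexol is still circulating when the study dose is given, the measured curve carries both doses and the numerator carries one. The ratio is then too small. Slow clearance leaves more residue, so the error is largest where GFR is low. That is the range for which section 4 justifies measuring GFR rather than estimating it.

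The index value enters three analyses in section 6: the 1-year decline (primary outcome a), the comparison of iohexol GFR with estimated GFR (outcome b), and the Cox model on day-14 GFR. Contrast from the index stay will be gone at one year, so the errors at the two visits do not cancel. In an affected patient the decline is understated and could look like recovery.

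**Working it through.** **Plan's own figure.** The documents give no figure for carry-over, so there is none to reproduce.

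**Inputs from the protocol**
- GFR = D/AUC and AUC = B/b, where D is the study dose (section 6).
- Post-injection samples at about 1, 2, 3 and 4 h (section 6).
- Clinical-to-study dose ratio R = 10 to 100, the inverse of 1/10 to 1/100 (section 7).
- Example GFR of 37 (section 4), used here as ml/min.

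**Assumptions not in the documents**
- One compartment, in line with the single exponential, with volume V = 18 L (varied below).
- The clinical agent was iohexol, given t hours before the study injection.
- True GFRs of 25 and 60 as further examples.

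**Derivation.** With k = GFR/V, the concentration just before injection is C0 = (R·D/V)·e^(-kt). After injection the total is (D/V + C0)·e^(-kX). The slope is unchanged, b = k, but B = D/V + C0. Hence

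GFR read = true GFR / (1 + r), with r = R·e^(-GFR·t/V).

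**Worked case.** GFR 37, V = 18,000 ml, 48 h = 2,880 min: the exponent is 37 × 2,880 / 18,000 = 5.92 and e^(-5.92) = 0.00268. So r = 0.0268 (R = 10) or 0.268 (R = 100), and the readings are 37/1.0268 = 36.0 and 37/1.268 = 29.2.

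| True GFR | Hours since contrast | Read, R = 10 | Read, R = 100 |
|---|---|---|---|
| 37 | 24 | 24.4 | 6.0 |
| 37 | 48 | 36.0 | 29.2 |
| 37 | 72 | 36.9 | 36.5 (1.4% low) |
| 25 | 48 | 21.1 | 8.8 |
| 25 | 72 | 24.4 | 20.0 |
| 60 | 24 | 55.4 | 32.9 |
| 60 | 48 | 60.0 | 59.6 |

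**Sensitivity to V.** For GFR 37 at 48 h, the shortfall runs from about 1% (V = 15 L, R = 10) to 44% (V = 22 L, R = 100).

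**How long it lasts.** The error falls below 5% when r < 0.0526, that is, when t > (V/GFR)·ln(R/0.0526). At V = 15 L and R = 10 to 100, this is 22 to 31 h at GFR 60, 44 to 63 h at GFR 30, and 87 to 126 h at GFR 15. This is the basis for the window of about 1 to 5 days.

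**Ways the pre-injection sample could be used.** Take true GFR 30, V = 15 L, R = 100, 48 h, with a least-squares fit to the 1 to 4 h samples:
- ignored: 22.8
- subtracted from every later sample as a constant: 43.4, because the background is itself decaying
- subtracted as a background decaying at rate b: 30.0

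If every blood sample is taken literally and the pre-injection value enters the fit at time zero, the fit fails even when carry-over is negligible. With true GFR 60, V = 15 L, R = 10, 48 h, it returns -47.5.

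**Correction.** The background contributes C0/b to the area, so the study dose contributes B/b - C0/b = (B - C0)/b. Since B - C0 = D/V and b = GFR/V, D divided by this area is the true GFR. Also C0/B = r/(1 + r), which is exactly the fraction by which the uncorrected value is low.

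**The case against.** The strongest reply is that this is an unstated detail and not an error. Blood is drawn before the injection, detecting background is the obvious reason to draw it, and the citation after the formula is cut off in the available text, so the source method may specify a correction. This stands in part: the intended use of the sample is unknown. But the calculation as written is complete and gives a low value when residue is present, and the simple constant subtraction that an analyst might supply is also biased, in the other direction.

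Several stronger readings are tempting, and the documents do not support them.

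- **That most index GFRs are biased.** The safety plan gives neither the agent nor the date of the scans. The index test is near day 14 or ICU discharge, and a scan a week earlier leaves almost nothing: a true GFR of 15 reads 14.9 to 15.0 at 7 days (V = 15 L).
- **That the patients with the worst kidneys are hit.** Those on renal replacement therapy do not get the plasma method, and end-stage renal disease on admission is an exclusion. The exposed patients have low GFR and are off replacement therapy.
- **That the bias falls mainly on the chronic critical illness group.** Controls leave the ICU before day 14 and might be tested sooner after a scan. The net direction between groups is open.
- **That the error can be set against the planned difference of 6 ml/yr (12 versus 6).** At GFR 37 and 48 h the individual error is 1.0 ml (R = 10) or 7.8 ml (R = 100). A group mean moves only by that error times the share affected, which is unknown.

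Exposure is also diluted. Plasma iohexol is one of four optional methods, and the plan does not say which method's value enters outcome (a) or the Cox model.

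**Conclusion.** The point holds conditionally. As written, the plasma iohexol formula gives too low an index GFR whenever clinical iohexol remains in the blood. The error matters for iohexol given within about 1 to 5 days to a patient with low GFR who is not on replacement therapy. In such a patient it ranges from trivial to severe, depending on the interval, the dose ratio and the assumed volume. It understates that patient's decline in outcome (a), and distorts the iohexol comparison in (b) and the day-14 GFR in the Cox model. The individual figures rest on a one-compartment model and an assumed volume. The frequency and the net effect on the group comparison cannot be derived. Severity is moderate: the concentration needed for the correction is already collected, so the correction can be made at analysis.

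**What to change.** In section 6, under Iohexol clearance:

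1. State that the exponential is fitted to the post-injection samples only, and that AUC = (B - C0)/b, where C0 is the pre-injection concentration. Say explicitly that the background is treated as decaying and is not subtracted as a constant.
2. Record the agent, date and time of the last clinical contrast from the electronic medical record.
3. Prespecify a sensitivity analysis of outcomes (a) and (b) and the Cox model that leaves out iohexol GFRs where C0 is a material share of B, for example over 10%. When C0 is large, B - C0 is a small difference between two measured quantities, and even the corrected value is less reliable.

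The cost is one changed line in the formula and three recorded items. There is no extra sample or visit. The downside is that a few index values will be flagged.

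### Iohexol GFR is in raw ml/min while the estimated GFR is, on the protocol's own usage, per 1.73 m²; nothing puts them on one scale before they are correlated and used to validate the methods

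*Combined protocol and SAP*

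**What the plan says.** In section 6, Research Plan, item 1 (Iohexol clearance) fits a single exponential to the blood concentrations and integrates it to an AUC. It then states: "The GFR value (ml/min) is then obtained by dividing the administrated dose by the AUC". No body-size step follows, although the text stops at an unfinished reference. Item 2 (timed urine) works from volume and concentrations, also with no body-size step. Item 3 reads: "We will estimate GFR using both serum creatinine and cystatin C and average the two values using CKD-EPI equation". It prints no unit.

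The protocol does give a unit for a creatinine-based GFR in section 4, Background, where the worked example "would reflect glomerular filtration rate of ~ 37 mL/min/1.73 m²".

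The paragraph after item 3 sets the two side by side: "The measured iohexol glomerular filtration rate will be compared to the estimated glomerular filtration rate". The only adjustment named is "in order to correlate the equation after adjusting for loss of muscle mass". Primary outcome (b) is the correlation of these two quantities, and the Background presents iohexol as the gold standard for validating the other methods.

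Primary outcome (a), the one-year decline by group, names no GFR method, while four methods joined by and/or are offered at each visit. The sample-size paragraph plans on an "average glomerular filtration rate decline of 6" with SD 16, in units of ml/yr. The documents nowhere mention body surface area (BSA), height or weight.

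**The concern.** Raw and indexed GFR differ by the factor BSA/1.73, which varies from patient to patient. If raw iohexol values are set against indexed estimates, two patients with the same indexed kidney function and different body size show different discrepancies even when the equation is perfect for both. A validation done this way blames the equation for body size. The muscle-mass adjustment does not cure this, because it addresses creatinine generation and not the unit of the iohexol value.

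At stake are the size of the correlation in outcome (b) and, more visibly, any statement on bias or agreement from the validation. Outcome (a) is exposed only in a narrower way: if a patient's two visits are on different scales, the difference between them contains the conversion factor as well as the change in kidney function.

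**Working it through.** **Inputs from the documents.** Iohexol GFR in ml/min (section 6, item 1). Creatinine-based GFR per 1.73 m² (section 4). Decline of 6 in controls and two-fold, i.e. 12, in chronic critical illness; SD 16; 80 controls and 150 cases; two-sided 0.05; stated power 80% (Sample size and feasibility).

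**Assumptions.** The documents give no BSA, so every BSA value here is assumed. So are the spread of GFR, the 20% error of the equation, and the independence of BSA from indexed GFR.

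**1. The plan's own figure.** SE = 16 × √(1/80 + 1/150) = 2.215. Then 6/2.215 = 2.709, and 2.709 − 1.960 = 0.749, which gives power of 77.3% (77.0% with the noncentral t) against the stated 80%. This shortfall is separate from the unit question. Power depends on 6/16, so relabelling ml/yr does not change it.

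**2. Conversion.** Raw = indexed × BSA/1.73. An indexed GFR of 60 reads:

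| Assumed BSA (m²) | Raw (ml/min) |
|---|---|
| 1.6 | 55.5 |
| 1.9 | 65.9 |
| 2.0 | 69.4 |
| 2.2 | 76.3 |

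**3. Outcome (b).** Write c for a coefficient of variation.

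- Same scale: r = c_GFR / √[(1 + c_GFR²)(1 + c_err²) − 1], where c_err² = exp(0.2²) − 1 = 0.0408.
- Mixed scales: multiply that r by c_GFR / √[(1 + c_GFR²)(1 + c_BSA²) − 1].

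Example: indexed GFR 60 ± 25 and BSA 2.0 ± 0.25, so c_GFR = 0.4167 and c_BSA = 0.125.

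- Same scale: 0.4167/√(1.1736 × 1.0408 − 1) = 0.885.
- Factor: 0.4167/√(1.1736 × 1.0156 − 1) = 0.951.
- Mixed scales: 0.885 × 0.951 = 0.842, a loss of 0.043.

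A simulation with one million draws per setting gives the same values:

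| BSA (mean ± SD) | Indexed GFR | r, same scale | r, raw vs indexed | Mean raw − indexed |
|---|---|---|---|---|
| 1.9 ± 0.15 | 60 ± 25 | 0.885 | 0.867 | 5.9 |
| 1.9 ± 0.15 | 80 ± 30 | 0.867 | 0.846 | 7.9 |
| 2.0 ± 0.25 | 60 ± 25 | 0.885 | 0.842 | 9.4 |
| 2.0 ± 0.25 | 80 ± 30 | 0.867 | 0.817 | 12.5 |
| 2.1 ± 0.30 | 60 ± 25 | 0.885 | 0.830 | 12.8 |
| 2.1 ± 0.30 | 80 ± 30 | 0.867 | 0.803 | 17.1 |

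The loss in correlation runs from 0.018 to 0.064.

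**4. Outcome (a).** Simulated with BSA 2.0 ± 0.25 and 5,000 trials per row:

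| Situation | Power | Mean group difference |
|---|---|---|
| All indexed | 77% | 6.0 |
| Half raw, half indexed, each patient on one scale throughout | 76% | 6.5 |
| 10% go from raw to indexed | 74% | 6.4 |
| 20% go from raw to indexed | 72% | 6.4 |
| 30% go from raw to indexed | 70% | 6.3 |

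In the last three rows, switchers had an assumed baseline indexed GFR of 60 ± 20. The simulation error is about √(0.77 × 0.23/5000) = 0.6 points, so the first two rows are hardly distinguishable. For one switching patient at BSA 2.0 m² with indexed GFR constant at 60, the apparent decline is 69.4 − 60 = 9.4.

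**5. Effect of indexing to each visit's weight.** Suppose raw GFR stays at 60 ml/min and BSA falls from 2.0 to 1.9 m² (assumed). Indexed GFR goes from 60 × 1.73/2.0 = 51.9 to 60 × 1.73/1.9 = 54.6. That is an apparent gain of 2.7 with no change in clearance, against a planned group difference of 6.

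**The case against.** **The indexed side is inferred.** Item 3 prints no unit for the estimate. The per-1.73 m² scale rests on the Background example, which does not name CKD-EPI, and on the usual output of that equation. The text is also broken at two relevant places: the iohexol formula ends in an incomplete reference, and words are missing from the sentence on the comparison. A normalisation step could have stood there. This stands as a caveat. It does not settle the matter the other way, because the one explicit iohexol rule is raw and no conversion is stated anywhere.

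**Outcome (b) is a correlation.** A constant factor cannot move it; only the spread of BSA does, and the loss is modest. This stands. The level shift of 6 to 17 units matters for bias and agreement, which are not listed outcomes, though the stated aim of validating methods would naturally call on them.

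**Stronger readings a reader might infer.** One is that the plan pools methods in outcome (a). It does not say so. The text speaks of comparing the one-year value with the measured value at discharge, and of measuring and estimating GFR in all patients. Pooling and switching are left open because outcome (a) names no method, and neither is planned. Another is that the level gap, about 16 ml/min at BSA 2.2 m² and indexed GFR 60, matches the planning SD of 16. Those are different quantities: one is a difference in level, the other the SD of a one-year change. For a patient who keeps one scale, the level gap does not enter the change as an offset; the change is only rescaled.

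**Simple indexing could do harm.** The Background expects marked muscle loss. If body weight falls with it, visit-by-visit indexing can hide decline, and do so unequally if cases lose more weight than controls. This stands and shapes the fix.

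**Conclusion.** The concern holds for outcome (b) and for the validation of methods. As written, a raw iohexol clearance is set against an estimate that the protocol's own usage places per 1.73 m², so body-size variation appears as estimation error. Under the assumed BSA distributions the correlation loses about 0.02 to 0.06, and raw values lie 6 to 17 units above indexed ones on average.

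For outcome (a) the finding is limited. With one scale per patient the cost is about one point of power. A loss of 3 to 7 points arises only if an assumed 10 to 30% of patients change scale between visits, which the documents neither plan nor exclude. The ml/yr label leaves the scale of the planning decline undefined but does not affect the power calculation.

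These sizes rest on BSA, GFR spread and equation error that the documents do not supply, and on reading the CKD-EPI estimate as indexed. The point is worth settling before analysis because it concerns a primary outcome and costs little to correct.

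**What to change.** - **Outcome (b) and the validation of methods:** convert both values to one scale. Either index the iohexol and urinary clearances to 1.73 m², or de-index the estimate. Use height and weight from the same visit and a named BSA formula. State the unit of the CKD-EPI value.
- **Outcome (a):** compute each patient's decline on one scale at both visits, and never subtract an indexed value from a raw one. Report the decline unindexed, or indexed to one fixed BSA per patient, alongside any visit-indexed result.
- **Sample size:** state the planning decline and its SD in the chosen unit.

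The cost is a short derivation rule and two variables. Height and weight must be available at each visit, which the documents do not confirm, and ICU weight may include retained fluid, so the plan should say which weight is used.
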